15.3. Secondary Aim 1 (PCORI-specified Primary Aim)

An important secondary aim and the primary aim for PCORI is the number of discussions related to geriatric domains, as measured by the GA, brought up during the audio-recorded baseline visit. In our preliminary data from a multicenter study, the median number of discussions was 1 in 32 audio-recorded conversations between older patients, their caregivers, and oncology physicians. This preliminary work has allowed us to calculate the intracluster correlation (ICC) amongst 8 different sites for the assessment of the secondary outcome, number of discussions related to geriatric domains. The ICC was 0.122 with a 95% confidence interval from 0.008 to 0.659. Because of the large amount of uncertainty in the ICC, we calculated power curves for $ICC = \{0.008, 0.122, 0.659\}$, with $ICC = 0.659$ being the most conservative. This design (with 8 NCORP sites per arm and 31 evaluable subjects per NCORP) has 80% power at the 0.05 significance level to detect a change of 0.235, 0.456 and 0.962 in the mean number of discussions for $ICC = \{0.008, 0.122, 0.659\}$ respectively, assuming a standard deviation of 0.78 (Figure 4). Since the best estimate of the ICC is 0.122, the expected detectable difference is 0.122. This corresponds to an effect size of 0.59.

Figure 4: Sample Size for Secondary Aim 1 (PCORI-specified Primary Aim)

The analysis for Secondary Aim 1 will be the same as for Primary Aim 1, but will use the number of discussions of age-related concerns as the response.

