1.8.5. The research team has experience with the assessment of patient-physician communication (using audio-recordings, surveys, and chart reviews) in the setting of advanced cancer. [name], an expert in patient-centered communication and co-investigator on this study, has conducted multi-method research to study patient-physician interactions using analyses of patient and physician surveys and medical record audits.⁷⁶ His research team has helped to establish that patient-centered communication is associated with improved information exchange, reduced symptom burden, lower health-care costs, and greater patient involvement in decision making.⁷⁷⁻⁷⁹ The measures to assess decision making in [name] NCI-funded RO1 ([name] is a co-investigator) have been adapted for patients with advanced cancer.^{67,68} Using two trained coders, we examined the audio-recorded interactions between the older patients (n=32) with advanced cancer and their oncology physicians (at 8 different sites) to assess number of discussions related to geriatric domains brought up by patient and/or caregiver that were addressed by the oncology physician and the number of "missed opportunities" (i.e., concerns brought up by patients and caregivers that were not adequately addressed by the oncology physician). We found that at baseline, there were 26 discussions and 26 missed opportunities among 32 audio-recorded visits. Fifty percent of visits had 0 age-related discussions; the median was 1 (range 1-3). The majority of missed opportunities were related to functional ability (e.g., not taking medicines correctly), physical functioning (e.g., inability to climb stairs, falls), social support (e.g., difficulty getting to appointments), and medications (e.g., polypharmacy, drug interactions). This study was not elderly specific and did not incorporate GA (which can identify deficits as described above), but the results provide an estimate of the baseline number of discussions about age-related issues that occur in usual care within oncology. We were able to utilize this data to help gather usual care information to inform our analytic plan.

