**3.4.2 Sample Size for PCORI-Specified Primary Aim**

The primary focus for the PCORI analysis is the number of discussions related to geriatric domains, as measured by the GA, brought up and addressed during the audio-recorded baseline visit. In our preliminary data from a multicenter study, the median number of discussions was 1 in 32 audio-recorded conversations between older patients, their caregivers, and oncology physicians. This preliminary work allowed us to calculate the intracluster correlation (ICC) amongst 8 different sites for the assessment of the secondary outcome, number of discussions related to geriatric domains. The ICC was 0.122 with a 95% confidence interval from 0.008 to 0.659. Because of the large amount of uncertainty in the ICC, we calculated power curves for ICC={0.008, 0.122, 0.659}, with ICC=0.659 being the most conservative. This design (with 8 NCORP sites per arm and 31 evaluable subjects per NCORP) has 80% power at the 0.05 significance level to detect a change of 0.235, 0.456 and 0.962 in the mean number of discussions for ICC={0.008, 0.122, 0.659 } respectively, assuming a standard deviation of 0.78 .

Since the best estimate of the ICC is 0.122, the expected detectable difference is 0.122. This corresponds to an effect size of 0.59.

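### The pilot figures behind the PCORI primary endpoint do not agree: half of visits at zero and 26 discussions in 32 visits rule out a median of 1 and an SD of 0.78 over all 32 visits

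*Protocol*

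**What the plan says.** Protocol 1.8.5 describes the pilot recordings: "there were 26 discussions and 26 missed opportunities among 32 audio-recorded visits". It then says: "Fifty percent of visits had 0 age-related discussions; the median was 1 (range 1-3". It presents these data as an estimate of usual care and as input to the analytic plan.

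Protocol 15.3 carries forward only part of this: "the median number of discussions was 1 in 32 audio-recorded conversations between older patients, their caregivers, and oncology physicians". SAP 3.4.2 repeats that "the median number of discussions was 1 in 32 audio-recorded conversations". Neither section mentions the visits with no discussion.

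The power statement in both documents takes the ICC from the pilot ("The ICC was 0.122 with a 95% confidence interval from 0.008 to 0.659"), uses a design "with 8 NCORP sites per arm and 31 evaluable subjects per NCORP", and is made "assuming a standard deviation of 0.78". The design "has 80% power at the 0.05 significance level to detect a change of 0.235, 0.456 and 0.962 in the mean number of discussions" across the three ICC values. No source is given for 0.78.

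**The concern.** The endpoint counts discussions in every recorded visit, so visits with none belong in its distribution. A range of 1 to 3 cannot hold over 32 visits when half of them are at zero. A median of 1 over all 32 visits does not fit 16 zeros either. This raises the question of which visits the median, the range and the SD describe.

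The SD matters most. Each stated detectable change is proportional to it, and these are the figures that support PCORI's primary aim. If 0.78 is too small for the all-visit count, the 16-site power statement is too favourable.

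**Working it through.** **Inputs.** Protocol 1.8.5: 32 visits, 26 discussions, 50% zeros, maximum 3. Protocol 15.3 and SAP 3.4.2: SD 0.78; ICC 0.008, 0.122 and 0.659; k = 8 sites per arm; m = 31 per site; 80% power; alpha 0.05 (taken as two-sided, which reproduces the plan).

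**Step 1: reproduce the plan.** Detectable change = (t[14, 0.975] + t[14, 0.80]) × SD × √(2[1 + (m − 1)ICC]/(km)), where the t quantiles sum to 2.145 + 0.868 = 3.013.

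- ICC 0.008: 3.013 × 0.78 × √(2 × 1.24/248) = 0.235
- ICC 0.122: 3.013 × 0.78 × √(2 × 4.66/248) = 0.456
- ICC 0.659: 3.013 × 0.78 × √(2 × 20.77/248) = 0.962

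All three match, so the formula is right for its inputs. The effect size also follows: 0.456/0.78 = 0.585, given as 0.59.

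**Step 2: range and median on the 1.8.5 counts.** With 26 discussions in 32 visits, at most 26 visits can be non-zero, so at least 6 are zero and the range cannot start at 1. With 16 zeros, the 16th and 17th ordered values are 0 and 1, so the median is 0.5. The mean is 26/32 = 0.81.

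**Step 3: SD on the 1.8.5 counts.** Let z be the number of visits with 0 discussions and c the number with 3. With 32 visits, 26 discussions and a maximum of 3, the sum of squares is 14 + 2z + 2c. The SD (divisor n − 1) is √((14 + 2z + 2c − 26²/32)/31), where 26²/32 = 21.125. At z = 16 there are six possible distributions:

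| Visits with 1 / 2 / 3 | Median of non-zero visits | All-visit SD | Detectable change, ICC 0.122 | Power at 0.456 |
|---|---|---|---|---|
| 6 / 10 / 0 | 2 | 0.896 | 0.523 | 69% |
| 7 / 8 / 1 | 2 | 0.931 | 0.544 | 65% |
| 8 / 6 / 2 | 1.5 | 0.965 | 0.564 | 62% |
| 9 / 4 / 3 | 1 | 0.998 | 0.583 | 59% |
| 10 / 2 / 4 | 1 | 1.030 | 0.602 | 57% |
| 11 / 0 / 5 | 1 | 1.061 | 0.620 | 54% |

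The first row has no visit with three discussions, so it does not fit the stated maximum. With a 3 present the SD is at least 0.93. If the median of 1 refers to the non-zero visits, it is 1.00 to 1.06. An SD of 0.78 cannot be reached.

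**Step 4: can a median of 1 and an SD of 0.78 describe all 32 visits?** An SD that rounds to 0.78 needs a sum of squares of 40: √((40 − 21.125)/31) = 0.780. That means z + c = 13. The feasible splits (visits with 0 / 1 / 2 / 3) are 11/18/1/2, 12/15/4/1 and 13/12/7/0. Each has 26 discussions and a median of 1. So Protocol 15.3 is attainable by itself, but with 11 to 13 zeros rather than 16.

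**Step 5: the current number of sites.** Protocol 15.2 and SAP 3.4.1 report 68 sites. Assume equal sizes, each site a separate cluster, and 16 × 31 = 496 evaluable patients. Then k = 34, m = 496/68 = 7.29 and df = 66. At ICC 0.122 the detectable change is 0.339 × SD, which is 0.265 at SD 0.78, 0.316 at 0.93 and 0.360 at 1.06.

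**The case against.** A reader might infer that 0.78 is the SD of the 16 non-zero visits, that the zeros were therefore dropped, and that the plan's SD is proven too small. The documents do not support going that far.

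- The match rests on the 9/4/3 split, which gives 0.781 only with divisor n; the usual sample SD is 0.806. The all-visit splits in step 4 reach 0.780 with the usual divisor.
- Both documents call 0.78 an assumption and do not tie it to the pilot.
- Nothing in Protocol 15.3 or SAP 3.4.2 is impossible by itself. The conflict appears only alongside the 50% and the range in 1.8.5.
- The median turns on one visit: with 15 zeros it would be 1. The SD is less sensitive, since 15 zeros and at least one 3 still give 0.90 or more.
- The counts may be different variables. Protocol 1.8.5 counts topics raised by patients or caregivers and addressed by the physician, Protocol 15.3 counts topics brought up, and SAP 3.4.2 counts topics brought up and addressed.
- The pilot was not specific to older patients, whereas trial patients must have a geriatric impairment. A corrected pilot SD is therefore not necessarily the trial's SD.
- The zeros are disclosed in Protocol 1.8.5. The sample-size sections omit them; the protocol as a whole does not hide them.

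All of this stands, and it limits the diagnosis. It does not remove the inconsistency. On either reading at least one published figure is wrong or unlabelled, and no other section resolves it.

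**Conclusion.** The point holds as an unresolved inconsistency. Protocol 1.8.5 contradicts itself, and its counts conflict with the median and SD in Protocol 15.3 and SAP 3.4.2. There are two readings.

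- **The 50% zeros and 26 discussions are right.** The all-visit median is 0.5, the range starts at 0, and the SD is 0.93 to 1.06 with a maximum of 3. At ICC 0.122 in the 16-site design the detectable change is about 0.54 to 0.62, which is 19% to 36% above the stated 0.456. Power at 0.456 falls from 80% to between 65% and 54%.
- **The median of 1 and SD of 0.78 describe all 32 visits.** The detectable changes stand, and the 50% and the range in 1.8.5 are wrong.

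The range of 1 to 3 suggests that the median and range describe only visits with at least one discussion, but that is an inference. The practical effect is modest. Under the step 5 assumptions the 68-site detectable change stays below 0.456 even at SD 1.06. Unequal site sizes, or sites that are not separate clusters, would raise it.

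**What to change.** Reconcile Protocol 1.8.5, Protocol 15.3 and SAP 3.4.2 from the pilot data:

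1. Give the frequency table (visits with 0, 1, 2 and 3 discussions) and the mean, median, range and SD over all 32 visits.
2. State where 0.78 comes from, including which visits it covers and whether it is a pilot estimate or a planning assumption.
3. Label any statistic that is conditional on at least one discussion.
4. State whether the pilot count is the same variable as the trial endpoint.
5. Restate the detectable changes with the verified all-visit SD, preferably for the current number of sites as well.

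Replacement values such as a median of 0.5 or an SD near 1.0 should not be written in until the pilot counts confirm them. The same edit can correct a separate slip in both sample-size sections, where the expected detectable difference is given as 0.122. That repeats the ICC; the plan's own figure is 0.456.

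The cost is text in three sections and one look-up in the pilot data. The stated detectable change may become less favourable. Enrolment and data collection do not change.

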15.4. Other Secondary Analyses

15.4.1. Secondary Aim 2: HRQoL will be assessed with the FACT and Caregiver HRQoL will be assessed with the Caregiver Reactions Assessment (CRA). The analysis will be the same as that used for Primary Aim 1. We will include geriatric assessment impairment (at baseline and follow up) to evaluate if these influence patient-reported HRQoL differently in the intervention versus the control group. We will also compare whether the uptake of geriatric assessment recommendations influences patient reported HRQoL and caregiver burden. Data from the intervention arm will be fit to a linear mixed model with FACT or CRA as the outcome, number and percent of implemented interventions (number implemented/number recommended) as the fixed effect, and NCORP site as a random effect independent of residual error. Analyses will be adjusted for treatment status.

15.4.2. Secondary Aim 3: We will compare the effect of the intervention on caregiver satisfaction (the modified health care climate questionnaire for the caregiver) using the same linear mixed model methodology.

15.4.3. Exploratory Aims: Exploratory aims will evaluate (1) whether the number of discussions about age-related issues during the clinic visit correlates with patient satisfaction, (2) whether the intervention increases the proportion of age-related concerns that are acknowledged and addressed, and (3) if communication about age-related issues influences how patients, caregivers, and oncology physicians make decisions for cancer treatment. An additional exploratory aim will examine the impact of the intervention on survival.

In order to examine the relationship between observed communication from audio-recordings and patient satisfaction, we will evaluate the correlation between the numbers of discussions regarding age-related concerns from audio-recorded visits with patient satisfaction on HCCQ-age (modified to evaluate for satisfaction for communication about age-related issues). We will determine the association of baseline oncology physician and patient decision-making preferences on the likelihood of having a discussion related to geriatric domains. The analysis for PCORI Primary Aim (secondary aim 1) will be used with the above characteristics added as independent variables. The statistical significance and estimated coefficients will be used to identify and interpret potentially important baseline features. Any conclusions will be considered to be hypothesis generating for further research.

We will also measure the intervention increases the proportion of age-related issues that are acknowledged and addressed (e.g., oncology physician response/(number of patient and caregiver concerns). We will examine if the intervention improves physician confidence with managing age-related conditions as well as physician comfort with communication about age-related issues (using data from physician baseline and follow up forms)

We will capture survival through the participant's medical record and verification with the primary team. We will follow participants for survival for 12 months after enrollment. We will obtain the date, location of death, and cause of death. If a site becomes aware that a study participant is deceased, they should complete the withdrawal form if the survival status form is not yet available on the URCC NCORP website. Otherwise sites will be contacted approximately 1 year after each participant was enrolled to assess survival and asked to complete this form. We will determine the effect of the intervention on 12-month survival using log rank tests and survival plots.

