Due to the coding schema involving a conditional coding structure, inter rater reliability involved percent agreement in 3 coding areas: number of geriatric concerns, the category of geriatric domain discussed, and the physician's response quality. *A GA communication composite score will be created by adding all GA-related topics that were discussed for each visit.* For number of geriatric concerns, the percent agreement was calculated using the difference in numbers between each coder and the consensus. An average of all coder agreement was calculated for the category of geriatric domain and physician response quality. If inter-rater agreement percentages fell below 70%, the coding team would meet for additional training. The principal investigator remained involved in the coding process and provided guidance or adjudication when necessary.

Another secondary outcome measure will be patient-reported HRQoL as measured by the FACT and caregiver HRQoL (burden) as measured by the Caregiver Reactions Assessment (CRA). We hypothesize that the mean HRQoL for patients and caregivers at sites randomized to the intervention arm will be higher than for those in the usual care arm at 4-6 weeks following the intervention and that this increase will be both statistically significant and clinically meaningful.^{99,100} We will include GA impairment (at baseline and follow up) to evaluate if these influence patient-reported and caregiver-reported HRQoL differently in the intervention versus the control group. Other secondary outcomes will include whether the intervention impacts how the oncology physician acknowledges and addresses age-related concerns, caregiver burden (as measured by the Caregiver Reaction Survey) and caregiver satisfaction with communication (as measured by the modified HCCQ) at 4-6 weeks. We will follow participants for survival for 12 months after enrollment. We will obtain the date, location of death, and cause of death. If a site becomes aware that a study participant is deceased, they should complete the form which is available on the URCC NCORP website. Otherwise sites will be contacted approximately 1 year after each participant was enrolled to assess survival and asked to complete this form.

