8.1. Components of Geriatric Assessment (Patient)

Assessment tools comprising the comprehensive GA are listed in **Table 2**. The various assessment tools were selected based upon extensive data in the geriatric literature demonstrating predictive value as well as feasibility data in multiple studies of elderly patients with cancer. Other than the cognitive and physical performance measures, the assessments are self-administered. Patients who cannot complete the assessment on their own will receive assistance from study personnel or from a caregiver. The GA is performed before baseline registration. Follow-up GA measures are collected at 4-6 weeks, 3 months, and 6 months.

Table 2: Components of the Comprehensive Geriatric Assessment

DOMAIN	TOOL	SCORE SIGNIFYING IMPAIRMENT
Physical function	
 ➤ Activities of Daily Living ➤ Instrumental ADLs ➤ Fall History ➤ OARS Physical Health 	
 ➤ Any ADL deficit ➤ Any IADL deficit ➤ Any history of falls ➤ A lot of difficulty with any task
Objective physical performance	
 ➤ Short Physical Performance Battery ➤ Timed “Up and Go”*** 	
 ➤ ≤ 9 points ➤ >13.5 seconds
Comorbidity	
 ➤ OARS Comorbidity*** 	
 ➤ Patient answered “yes” to ≥3 chronic illnesses ➤ One illness interferes “a great deal” with QoL
Nutrition	
 ➤ Body Mass Index ➤ Mini Nutritional Status*** ➤ Weight loss*** 	
 ➤ <21 kg/m² ➤ ≤ 11 points ➤ >10% from baseline weight
Social support	
 ➤ OARS Medical Social Support*** 	
 ➤ Patient answers one of the social support questions indicating less than adequate support for care
Polypharmacy	
 ➤ Polypharmacy ➤ Lab*** 	
 ➤ ≥5 regularly scheduled prescription medications OR ➤ Any high-risk medication OR ➤ Creatinine clearance <60 ml/min
Psychological	
 ➤ GAD-7 *** ➤ Geriatric Depression Scale 	
 ➤ ≥ 10 points ➤ ≥5 points
Cognition	
 ➤ Blessed OMC*** ➤ Mini-Cog 	
 ➤ >10 ➤ 0 words recalled OR 1-2 words recalled + abnormal clock drawing test

***Captured before baseline registration

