15. STATISTICAL PLAN

15.1. Statistical Considerations

[figure not shown]
This is a cluster-randomized trial with NCORP practice sites being the clusters. Because of the cluster randomized study design, we will apply linear mixed model methodology.¹⁰⁴ The outcome will be the response, and the arm will be the fixed effect. NCORP practice sites will be entered as a random effect independent of residual error. Estimation will be performed using Restricted Maximum Likelihood, and the null hypothesis of zero mean difference between arms will be tested using a F test.¹⁰⁵ The specific NCORP practice site differences will be assessed graphically using Best Linear Unbiased Predictors (BLUP) of the mean response for each NCORP.

All regression analyses will include terms to control for study site and oncologist type. In addition, clinically important socioeconomic variables such as patient gender, age, race/ ethnicity, and cancer variables such as cancer type and treatment status will be used to control for patient-level covariates. In case a key covariate is found to be unbalanced between study arms, it will be included in the model as a potential confounder.

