Analysis for Primary Aim 1. This is a cluster randomized trial with NCORP practice sites being the clusters. Because of the cluster randomized study design, we will apply linear mixed model methodology.¹⁰⁴ The total modified HCCQ scores (HCCQ-age) will be the response, and the arm will be the fixed effect. NCORP practice sites will be entered as a random effect independent of residual error. Estimation will be performed using Restricted Maximum Likelihood, and the null hypothesis of zero mean difference between arms will be tested using the F test.¹⁰⁵ The specific practice site differences will be assessed graphically using Best Linear Unbiased Predictors (BLUP) of the mean response for each site.

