A CRA will audio-record the patient-oncologist consultation. This visit must occur after the geriatric assessment is completed and before treatment initiation. A medical consultation should be scheduled prior to start of cancer treatment (if planned). We will assess the number of age-related concerns brought up by patients and caregivers. We will also assess how the physician addresses these concerns. Our team has experience with all of the study measures. **Transcriptionists** will transcribe all audio-recorded visits and will be blinded to study condition. **Coders** will undergo extensive training and supervision by developers of the scales. Transcriptionists and coders will not be part of the study team or involved in any other aspects of the study, and will be blinded to study hypotheses and site assignments to intervention or control. Further, during analysis, study team members will be blinded to site assignments of intervention or control.

TABLES OF DATA TO BE KEPT

Table 1: Patient Measures

Measure	Aim	Screening Visit 00	Baseline Visit 01	Telephone Team Call ^a	4-6 Weeks Visit 02	3 Months Visit 03	6 Months Visit 04
Demographics		Pt					
ADL	GA	Pt			Pt	Pt	Pt
IADL	GA	Pt			Pt	Pt	Pt
Fall History	GA	Pt			Pt (f/u)	Pt (f/u)	Pt (f/u)
OARS Physical Health	GA	Pt			Pt	Pt	Pt
OARS Comorbidity	GA	Pt					
OARS Medical Social Support	GA	Pt					
Social Activities	GA	Pt			Pt (1 item)	Pt (1 item)	Pt (1 item)
GAD-7	GA	Pt					
GDS	GA	Pt			Pt	Pt	Pt
Patient-rated KPS	S2	Pt			Pt	Pt	Pt
HCCQ	P1			Pt	Pt	Pt	Pt
HCCQ-age	P1			Pt	Pt	Pt	Pt
Press-Ganey Pt Satisfaction	P1				Pt	Pt	Pt
FACT	S2		Pt		Pt	Pt	Pt
MDASI	S2		Pt		Pt	Pt	Pt
Emotional Distress	S2	Pt			Pt	Pt	Pt
PEACE	E		Pt		Pt		
PEPPI	E		Pt		Pt		
Control Preferences Scale	E		Pt				
MUIS- Complexity Subscale	E		Pt		Pt	Pt	Pt
Understanding of Disease	E		Pt		Pt		
Survey Completion		Pt			Pt	Pt	Pt

Note: Screening and baseline can be combined. ^a A research staff member from the Telephone Team will call the patient within 1 to 7 days after the baseline audiorecorded visit.

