Abbreviations: Pt (Patient); Phys (Physician); GA (Geriatric Assessment); P1 (Primary Aim 1); E (Exploratory Aim); S2 (Secondary Aim 2); ADL (Activities of Daily Living); IADL (Instrumental Activities of Daily Living); GAD (Generalized Anxiety Disorder 7-Item Scale); Geriatric Depression Scale (GDS); KPS (Karnofsky Performance Status); PEACE (Peace, Equanimity, and Acceptance in the Cancer Experience); PEPPI (The Perceived Efficacy in Patient-Physician Interactions); MUIS (Mishel Uncertainty in Illness Scale); CTSQ (Cancer Treatment Satisfaction Questionnaire); FACTF (Functional Assessment of Chronic Illness Therapy); MDASI (MD Anderson Symptom Inventory).

Table 2: Caregiver Measures

Measure	Aim	Screening Visit 00	Baseline Visit 01	Telephone Team Call ^a	4-6 Weeks Visit 02	3 Months Visit 03	6 Months Visit 04
Demographics		C					
Caregiver Reaction	S2	C			C	C	C
OARS Comorbidity	S2	C					
SF-12	S2		C		C (f/u)	C (f/u)	C (f/u)
Cost of Care	S2	C			C	C	C
Ryff Environmental Mastery	S2		C		C	C	C
PHQ-2	S2		C		C	C	C
GAD-7 Anxiety	S2		C				
Health Care Climate Questionnaire-Communication (caregiver)	S3				C	C	C
HCCQ-age (patient)	S3				C	C	C
HCCQ-age (general, caregiver)	S3				C	C	C
Press-Ganey Pt Satisfaction	S3				C	C	C
Distress Thermometer	S2	C			C	C	C
PEACE	E		C		C		
PECPI	E		C		C		
Control Preferences Scale	E		C				
MUIS- Complexity Subscale	E		C		C	C	C
Understanding of Disease	E		C		C		
AD8	E	C			C (f/u)	C (f/u)	C (f/u)

Note: Screening and baseline can be combined. ^a A research staff member from the Telephone Team will call the patient within 1 to 7 days after the baseline audiorecorded visit.

Abbreviations: C (Caregiver); CRA (Clinical Research Associate); Pt (Patient); Phys (Physician); GA (geriatric assessment); P1 (Primary Aim 1); I (Intervention); E (Exploratory Aim); S1 (Secondary Aim 1); S2 (Secondary Aim 2); S3 (Secondary Aim 3); PEACE (Peace, Equanimity, and Acceptance in the Cancer Experience); PEPI (The Perceived Efficacy in Patient-Physician Interactions); MUIS (Mishel Uncertainty in Illness Scale); SF-12 (12-Item Short Form Health Survey); PHQ-2 (2-Item Patient Health Questionnaire); GAD (Generalized Anxiety Disorder 7-Item Scale); HCCQ (Health Care Climate Questionnaire); KPS (Karnofsky Performance Status); Blessed OMC (Blessed-Orientation Memory Concentration Test); SPPB (Short Physical Performance Battery).

Table 3: Clinical Research Associate & Physician Measures

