### 4.4 Other Secondary Analyses

#### 4.4.1. Secondary Aim 2

HRQoL will be assessed with the FACT-G and Caregiver HRQoL (burden) will be assessed with the Caregiver Reactions Assessment (CRA). We will include geriatric assessment impairment (at baseline and follow up) to evaluate if these influence patient-reported HRQoL differently in the intervention versus the control group. We will also compare whether the uptake of geriatric assessment recommendations influences patient reported HRQoL and caregiver burden. Data from the intervention arm will be fit to a linear mixed model with the FACT-G or CRA as the outcome, number and percent (number implemented/number recommended) of interventions as the fixed effect, and NCORP site as a random effect independent of residual error. Analyses will be adjusted for treatment status.

#### 4.4.2. Secondary Aim 3

We will compare the effect of the intervention on caregiver satisfaction (the modified health care climate questionnaire-age for the caregiver) using the same linear mixed model methodology.

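### Secondary Aim 2 (quality of life) does not name the collected baseline FACT or Caregiver Reaction score as a covariate, and examines GA impairment at follow-up, a post-intervention variable, for a differential influence by arm

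*Protocol*

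**What the plan says.** Protocol 15.4.1 defines the Secondary Aim 2 analysis by reference: "The analysis will be the same as that used for Primary Aim 1". The model referred to, under the Primary Aim 1 analysis in Protocol 15.2, is: "The total modified HCCQ scores (HCCQ-age) will be the response, and the arm will be the fixed effect". Practice site is the random effect, and estimation is by REML with an F test. SAP 4.4.1 does not repeat the cross-reference, so in the SAP the arm comparison rests on the general model of SAP 4.1.

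Protocol 15.1 and SAP 4.1 add terms for site and oncologist type, and give gender, age, race/ethnicity, cancer type and treatment status as examples of further covariates. Both then say: "In case a key covariate is found to be unbalanced between study arms, it will be included in the model as a potential confounder".

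The hypothesis in Protocol 7.2 is that mean quality of life of patients and caregivers in the intervention arm "will be higher than for those in the usual care arm at 4-6 weeks following the intervention". In Appendix X-1, "Table 1: Patient Measures" puts FACT at Baseline Visit 01, and "Table 2: Caregiver Measures" puts Caregiver Reaction at Screening Visit 00. Both scales are repeated at every follow-up visit.

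On geriatric assessment (GA) impairment, SAP 4.4.1 says: "We will include geriatric assessment impairment (at baseline and follow up) to evaluate if these influence patient-reported HRQoL differently" by arm. Protocol 15.4.1 says the same, and Protocol 7.2 extends it to caregivers. On timing, Protocol 8.1 states: "Follow-up GA measures are collected at 4-6 weeks, 3 months, and 6 months".

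**The concern.** The Primary Aim 1 model has no baseline outcome term for a good reason: HCCQ-age is first measured at the call after the visit. FACT and Caregiver Reaction do have baseline values, and a baseline value of the same scale is usually among the best predictors of the follow-up value. Reusing the primary model leaves that information out unless someone later judges the score to be a key covariate and out of balance. The plan defines neither term.

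The discretion matters more than usual here. There may be few independent clusters, so chance imbalance can be sizeable. Sites also learn their allocation once approved and trained (Protocol 9), before their staff recruit patients, so differential recruitment is possible too.

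The GA sentence raises a separate matter of interpretation. The intervention is meant to prompt action on the impairments found, so impairment recorded weeks later may itself depend on arm. Effects compared across follow-up impairment groups then do not compare like with like.

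**Working it through.** **Baseline score: what the text allows.** The Primary Aim 1 model contains no baseline outcome. The covariates named in Protocol 15.1 and SAP 4.1 do not include either score. Protocol 15.4.1 and SAP 4.4.1 add treatment status and GA impairment. That leaves the imbalance rule as the only stated route likely to bring the scores in.

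**Reproducing the plan's own figure.** No power figure is given for Secondary Aim 2. The nearest is the primary one in Protocol 15.2: 8 sites per arm, 31 subjects per site, SD 2.1, ICC 0.14, detectable difference 1.3.

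- SE in SD units = √(2[1 + 30 × 0.14]/(8 × 31)) = √(10.4/248) = 0.205.
- Detectable difference = (t₀.₉₇₅,₁₄ + t₀.₈₀,₁₄) × 2.1 × 0.205 = 1.30, or 0.617 SD. This agrees with the stated 1.3 and effect size 0.62.

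**Precision gain (illustrative).** The documents give no ICC for FACT or Caregiver Reaction and no correlation r between baseline and 4-6 weeks. Assumptions: r = 0.5 to 0.7; the HCCQ ICC of 0.14 with its limits 0.01 and 0.51; m = 31 per site for FACT; m = 0.8 × 31 = 24.8 for caregivers (SAP 3.3.3 expects about 80% of patients to have one).

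SE² = 2[ICC × f_b + (1 − ICC) × f_w/m]/k, with k = 8. Here f = 1 − r² (0.75 to 0.51) at each level that the baseline score explains, and 1 at a level it does not.

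- Within-site only, FACT, r = 0.5: (0.14 + 0.75 × 0.0277)/(0.14 + 0.0277) = 0.959; square root 0.979; SE cut 2.1%. At r = 0.7 the cut is 4.1%.
- Within-site only, Caregiver Reaction: 2.5% to 5.0%.
- Both levels, either scale: 1 − √0.75 = 13.4% to 1 − √0.51 = 28.6%.
- Within-site only at the ICC limits: FACT 10-21% and Caregiver Reaction 11-22% at ICC 0.01; under 1% for both at ICC 0.51.
- Detectable difference for FACT at ICC 0.14 and r = 0.6: 0.617 SD falls to 0.598 (within-site only) or 0.494 (both levels).

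These are upper figures for their scenarios. The formula compares with a model that has no covariates, whereas the plan already adjusts for several.

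**Chance imbalance in baseline FACT.** P(|difference| ≥ 0.2 SD) under a normal approximation, ICC 0.14, 496 patients:

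| Clusters | m | SE (SD) | Probability |
|---|---|---|---|
| 16 | 31 | 0.205 | 33% |
| 32 | 15.5 | 0.156 | 20% |
| 68 | 7.3 | 0.123 | 10% |

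With 16 clusters the probability is 5% at ICC 0.01 and 58% at ICC 0.51; with 68 it is 3% and 28%. The number of independent clusters cannot be derived. Protocol 15.2 counts 68 practice sites, but sites sharing staff take the same arm (Protocol 9), and randomisation IDs repeat across rows in SAP Appendix A. If the slope holds at both levels, a 0.2 SD difference moves an unadjusted estimate by r × 0.2 = 0.10 to 0.14 SD, and by less once the listed covariates are in.

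**Follow-up GA impairment.** The GA summary is handed over before the recorded visit (Protocol 10 and 11.3.2). Follow-up GA comes at 4-6 weeks or later, at the same visits as the outcome. A simulation with assumed parameters gave every patient the same true effect of 0.30 SD and let a common cause drive both follow-up impairment and quality of life. If the intervention left impairment unchanged, the effect within impairment groups stayed at 0.30. If it lowered latent impairment by 0.3 to 0.6 units (latent SD √2), the within-group effects fell to between 0.27 and 0.18, in both groups about equally. This shows the mechanism. It does not size the problem in this trial.

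**The case against.** The covariate lists are introduced as examples, so a baseline score is not excluded. That stands. A reader might infer that the plan rules the score out, and the text does not support that. An open list is still not prespecification.

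The gain may be small. It must be measured against a model that already holds demographic and cancer covariates and, in the quality-of-life analysis, baseline GA impairment. If baseline FACT explains only within-site variance, the gain is a few per cent at ICC 0.14. Imbalance also becomes rarer with more clusters. All of this stands, and the figures above are given as ranges and upper figures for that reason.

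Adjustment carries its own risk. Patient baseline surveys may be completed later on the visit day (Protocol 11.3.1b), after the GA summary has been received. Suppose a share p of intervention patients do this, and a fraction h of the 4-6 week effect appears at once. Adjustment then shrinks the estimate by about r × p × h: 0.6 × 0.2 × 0.5 = 6%, ranging from 0.5 × 0.1 × 0.25 = 1% to 0.7 × 0.5 × 1 = 35%, all assumed. This stands and shapes the fix. Caregiver forms are due before the visit (Protocol 11.2.2d), but Protocol 11.3.1b also allows completion on the day, so they are not wholly exempt.

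On follow-up GA, the documents ask only whether impairment influences quality of life differently by arm. They do not claim to identify who benefits. A reader might infer that a follow-up GA term enters the main arm comparison and biases it. The text does not say so, and the sentence reads naturally as a supplementary analysis.

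**Conclusion.** The point holds as a gap in prespecification for a named secondary aim. Neither baseline score is named, and its use is left to an undefined rule applied after the data are seen. A reader might infer that the randomised comparison is biased by the omission. It is not: the cost is precision, and discretion over chance or recruitment imbalance.

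Confidence is high on the omission and low on its size. With ICC 0.14 and 8 sites per arm, the standard error would fall by at most about 2-5% or 13-29%, depending on whether the baseline score explains site-level variance. The imbalance probability runs from about 33% to 10% as the number of independent clusters goes from 16 to 68. Both results rest on a borrowed ICC, and the precision gain also on assumed correlations.

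The follow-up GA analysis cannot show which patients benefit, because the grouping is recorded after the intervention. The baseline half of that sentence is sound. This limits how a supplementary analysis may be read. It does not by itself affect the main arm comparison, and it cannot be sized from the documents.

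**What to change.** In SAP 4.4.1:

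- Specify the 4-6 week FACT and Caregiver Reaction models as arm + baseline value of the same scale + the listed covariates, with site random. State that this is the arm comparison and that it contains no follow-up GA term.
- Keep participants with a missing baseline score by a stated rule applied identically in both arms, for example the mean pooled over arms.
- Test effect modification with baseline GA impairment × arm only. Label any follow-up GA analysis exploratory.
- For FACT, report two sensitivity analyses that need no completion time: the model without the baseline score, and one using patient-rated KPS and emotional distress from the screening packet instead. Protocol 11.3.1b and 11.3.2 place that packet before registration, and so before the GA summary is produced.
- Where timing is recorded, add a sensitivity analysis that treats baseline scores completed after receipt of the GA summary as missing. The cut-off is receipt of the summary, not the visit. Apply the same check to caregiver forms completed on the visit day. Because this missingness may differ by arm, it should not be the main analysis.

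The cost is SAP wording and one already collected covariate per model, with no change to accrual or visits. The downside is some attenuation of the FACT estimate if baseline scores follow the intervention, which the sensitivity analyses help to reveal.
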